4.3.2.2 Fulvestrant

Fulvestrant 500 mg will be administered in the clinic as two IM injections of 250 mg each on Days 1 and 15 of Cycle 1 and on Day 1 of each subsequent 28-day cycle until disease progression or intolerable toxicity. For more details regarding the dosing instructions and safety profile of fulvestrant, please refer to the fulvestrant (Faslodex[®]) Package Insert or Summary of Product Characteristics (SmPC).

The fulvestrant dose level cannot be modified. Guidelines for dosage modification and treatment interruption or discontinuation of fulvestrant are provided in Section 5.1.5.1.

Any overdose or incorrect administration of fulvestrant should be noted on the Fulvestrant Administration eCRF. Adverse events associated with an overdose or incorrect administration of fulvestrant should be recorded on the Adverse Event eCRF.

4.3.3 Investigational Medicinal Product Accountability

All investigational medicinal products (IMPs) required for completion of this study (GDC-0810 and fulvestrant) will be provided by the Sponsor where required by local health authority regulations. The study site will acknowledge receipt of IMPs using the IWRS to confirm the shipment condition and content. Any damaged shipments will be replaced.

IMPs will either be disposed of at the study site according to the study site's institutional standard operating procedure or returned to the Sponsor with the appropriate documentation. The site's method of IMP destruction must be agreed to by the Sponsor. The site must obtain written authorization from the Sponsor before any IMP is destroyed, and IMP destruction must be documented on the appropriate form.

Accurate records of all IMPs received at, dispensed from, returned to, and disposed of by the study site should be recorded on the Drug Inventory Log.

4.3.4 Post-Trial Access to GDC-0810

The Sponsor (Genentech) is a member of the Roche group and is subject to Roche's global policies. The Sponsor will offer post-trial access to the study drug (GDC-0810) free of charge to eligible patients in accordance with the Roche Global Policy on Continued Access to Investigational Medicinal Product, as outlined below.

A patient will be eligible to receive study drug after the end of the study if all of the following conditions are met:

- The patient has a life-threatening or severe medical condition and requires continued study drug treatment for his or her well-being
- There are no appropriate alternative treatments available to the patient
- The patient and his or her doctor comply with and satisfy any legal or regulatory requirements that apply to them

A patient will not be eligible to receive study drug after the end of the study if any of the following conditions are met:

- The study drug is commercially marketed in the patient's country and is reasonably accessible to the patient (e.g., is covered by the patient's insurance or wouldn't otherwise create a financial hardship for the patient)
- *The data suggest that the study drug is not effective for ER+ breast cancer*
- The Sponsor has reasonable safety concerns regarding the study drug as treatment for ER+ breast cancer
- Provision of study drug is not permitted under the laws and regulations of the patient's country

The Roche Global Policy on Continued Access to Investigational Medicinal Product is available at the following Web site:

http://www.roche.com/policy_continued_access_to_investigational_medicines.pdf

4.4 CONCOMITANT THERAPY

4.4.1 Permitted Therapy

Concomitant therapy includes any medication (e.g., prescription drugs, over-the-counter drugs, herbal or homeopathic remedies, nutritional supplements) used by a patient from 7 days prior to screening to the study completion/discontinuation visit. All such medications should be reported to the investigator and recorded on the Concomitant Medications eCRF.

Patients treated with anti-seizure medications should have levels monitored regularly.

Palliative and supportive care for disease-related symptoms may be administered at the investigator's discretion. Patients who experience toxicities should have their symptoms treated as clinically indicated. Anti-emetics and anti-diarrheal medications should not be

administered prophylactically before initial treatment with study drug. At the discretion of the investigator, prophylactic anti-emetic and/or anti-diarrheal medication(s) may be used as per standard clinical practice before subsequent doses of study drug.

Pain medications administered per standard clinical practice are allowed. Bone-sparing agents (e.g., bisphosphonates, denosumab) for palliation of bone metastases or for the treatment of osteoporosis/osteopenia are allowed, but initiation of such agents or modification of the pre-study bisphosphonate or denosumab treatment regimen require the approval of the Medical Monitor and should be avoided where possible.

GDC-0810 was shown to inhibit human CYP2B6 and CYP2C enzymes in vitro; therefore, drug-drug interactions with co-administered CYP2B6 and CYP2C substrates cannot be excluded and should be avoided where possible. Note that many of these medications are also metabolized by other CYP enzymes which are not inhibited by GDC-0810 (e.g., CYP3A4), thus attenuating the potential for drug-drug interactions to some extent. If there is clinical need for a particular CYP2B6 or CYP2C substrate drug, dose adjustments and/or use of alternative medications are recommended.

A list of possible CYP2B6 and CYP2C substrates can be found in [Appendix 9](#).

4.4.2 Prohibited Therapy

Use of the following concomitant therapies is prohibited for at least 14 days prior to Cycle 1 Day 1 dosing and during the study treatment:

- Therapy intended for the treatment of cancer (regulatory-approved or experimental), including chemotherapy, radiation therapy, immunotherapy, biologic therapy, herbal therapy, radiopharmaceutical therapy, or endocrine therapy.

Local radiotherapy is not permitted. It is understood that there may be extreme circumstances requiring local radiotherapy in which the investigator does not believe that the symptoms are a result of disease progression (e.g., impending fracture), and the radiation field does not encompass a target/non-target lesion. In such cases, the investigator must obtain approval from the Medical Monitor, and such patients should have a tumor assessment of the lesion(s) before they actually receive the radiotherapy. If a patient received radiation therapy and a target or non-target lesion is included in the field of radiation, the lesion(s) will become unevaluable for tumor response.

Further reasons for avoiding local radiotherapy include the difficulty in distinguishing new symptomatic pain or worsening of lytic bone lesions from disease progression. Radiation therapy to a specific site renders that lesion unevaluable for tumor response. Previous clinical experience also suggests that new bone pain is frequently a symptom of disease progression. Bone pain secondary to study treatment can be treated with pain medications, nonsteroidal anti-inflammatory drugs, or corticosteroids.

Use of the following concomitant therapies is prohibited for at least 7 days prior to Cycle 1 Day 1 dosing and during the study treatment:

- Hematopoietic growth factors (e.g., erythropoietins, G-CSF, and GM-CSF) are not to be administered prophylactically. Use of these agents should be reserved for cases of severe neutropenia and anemia per the labeling of these agents and require the approval of the Medical Monitor.
- Hormone replacement therapy, topical estrogens (including any intra-vaginal preparations), megestrol acetate and selective ER modulators (e.g., raloxifene) are prohibited.
- Owing to their narrow therapeutic index and the potential for drug-drug interactions, concomitant therapy with warfarin or phenytoin is prohibited. Please see [Appendix 9](#) for further information.

4.5 STUDY ASSESSMENTS

Please see [Appendix 1](#), [Appendix 2](#), and [Appendix 3](#) for the schedule of assessments performed during the study.

4.5.1 Informed Consent Forms and Screening Log

Written informed consent for participation in the study must be obtained before performing any study-specific screening tests or evaluations. Informed Consent Forms (ICFs) for enrolled patients and for patients who are not subsequently enrolled will be maintained at the study site.

All screening evaluations must be completed and reviewed to confirm that patients meet all eligibility criteria before randomization. The investigator will maintain a screening log to record details of all patients screened and to confirm eligibility or record reasons for screening failure, as applicable.

4.5.2 Medical History and Demographic Data

Medical history includes clinically significant diseases that have occurred within the previous 5 years before Cycle 1 Day 1, surgeries, breast cancer history (including tumor characteristics such as HR status, location of metastases, prior cancer therapies, surgeries and procedures), menopausal status, smoking history, and all medications (e.g., prescription drugs, over-the-counter drugs, herbal or homeopathic remedies, nutritional supplements) used by the patient within 7 days prior to the screening visit.

Demographic data will include age, sex, and self-reported race/ethnicity in accordance with the applicable laws (e.g., health authority requirements).

4.5.3 Physical Examinations

A complete physical examination should include an evaluation of the head, eyes, ears, nose, and throat, and the cardiovascular, dermatological, musculoskeletal, respiratory, GI, genitourinary, and neurological systems, as well as measurements of weight and

height (height is measured at screening only). Any abnormality identified at baseline should be recorded on the General Medical History and Baseline Conditions eCRF.

An assessment of the patient's ECOG Performance Status (see [Appendix 8](#)) will be completed at screening and as specified in the Schedule of Assessments (see [Appendix 1](#) and [Appendix 2](#)).

At subsequent visits (or as clinically indicated), symptom-directed physical examinations should be performed. Particular attention should be given to symptoms related to adverse events of special interest (e.g., diarrhea). Detailed information about any diarrhea symptoms (e.g., urgency, loss of stool continence, impact on lifestyle) as well as management (e.g., dietary changes, fluids, probiotics, use of anti-diarrheals) should be assessed. Changes from baseline abnormalities should be recorded in patient notes. New or worsened clinically significant abnormalities should be recorded as adverse events on the Adverse Event eCRF.

4.5.4 Vital Signs

Vital signs, collected at screening, *per institutional guidelines, and as clinically indicated* and at each subsequent visit, will include measurements of heart rate, systolic and diastolic blood pressure (while the patient is in a seated position), and oral or tympanic temperature.

4.5.5 Tumor and Response Evaluations

Tumor assessments will be performed at screening, *per institutional guidelines*, and when clinically indicated. All known measurable sites of disease must be documented at screening and re-assessed at each subsequent tumor evaluation. A documented standard-of-care tumor assessment performed within 28 days before Cycle 1 Day 1 may be used for the screening assessment, provided it meets the requirements described below.

Response assessments will be performed by the investigator, on the basis of physical examinations and imaging scans ([Appendix 7](#)).

CT scans are the preferred imaging modality for tumor assessments. Tumor assessments should include a diagnostic quality, contrast-enhanced CT scan of the chest, abdomen, and pelvis at baseline. CT scans of the neck should be included if clinically indicated. A CT for tumor assessment may be acquired on a PET/CT scanner if it is of full diagnostic quality and includes intravenous (IV) contrast.

In patients for whom a CT scan is contraindicated due to a CT IV contrast allergy, a CT of the chest without contrast and MRI of the abdomen and pelvis with contrast are recommended. MRI of the chest may only be performed with the approval of the Sponsor. In these patients, at screening, tumor assessments should include a

diagnostic quality, contrast-enhanced MRI scan of the chest (if approved), abdomen, and pelvis. MRI scans of the neck should be included if clinically indicated.

The same imaging method used at screening must be used throughout the study.

To be suitable for RECIST assessments, CT/MRI scans should ideally have a maximum thickness of 5 mm and minimal gaps. Subsequent tumor assessments should include CT/MRI scans of the chest, *pelvis*, and abdomen and other known sites of disease. In addition to the scheduled on-protocol CT/MRI scans, CT/MRI scans may be repeated at the investigator's discretion at any time if progressive disease is suspected.

A technetium bone scan should be performed at screening (up to 28 days prior to Cycle 1 Day 1) to evaluate for the presence of bone metastases. Positive areas on bone scans should be evaluated by X-ray, CT scan, or MRI prior to randomization (up to 28 days prior to Cycle 1 Day 1). Bone scans should be repeated in the event of clinical suspicion of progression of existing bone lesions, the development of new bone lesions, and in the assessment of a CR, if any disease was evident at screening. For adequate assessment of bone lesions, it is expected that the radiologist will adjust window leveling accordingly.

To ensure a valid comparison of tumor data and uniformity in the assessment of tumor response during the study, the following procedures must be implemented at the study site:

- All lesions identified at baseline (target and non-target) will be reassessed using the same method throughout the course of the study.
- All CT scans and MRIs obtained for all patients enrolled at the center should be reviewed by the local radiologist who, together with the investigator, will determine the local assessment of response and progression. All bone scans obtained from the patients with bone metastases should be reviewed similarly.
- All radiological data (CT scan, MRI and bone scan, etc.) and photos for skin lesions obtained at baseline, during treatment period and the follow-up period must be sent to a central imaging vendor contracted by the Sponsor within 2 weeks of imaging.
- Tumor response and progression will be assessed and will be the basis for the efficacy analyses (along with survival information). The main analysis of the trial will be based on the local radiology review results.

Patients who discontinue study treatment for any reason other than disease progression will continue to undergo tumor response evaluations until progressive disease or initiation of other anti-cancer therapy.

4.5.5.1 Response Evaluations in Patients with Bone-Only Disease

For patients with bone-only disease not visible on the CT or MRI scans being performed as part of the tumor assessments, a bone scan should be repeated at every tumor assessment (± 7 days for flexibility in the event of isotope shortage), and when clinically

indicated. Abnormalities found on subsequent bone scans should be evaluated by CT scan, MRI, or X-ray to ascertain the presence of bone destruction versus a healing reaction. In the absence of measurable disease at baseline, the following will be considered progression among patients with lytic or mixed (lytic + sclerotic) bone lesions:

- The appearance of one or more new lytic lesions in bone
- The appearance of one or more new lesions outside of bone
- Unequivocal progression of existing bone lesions

Pathologic fracture, new compression fracture, or bone metastasis complications will not be considered as evidence of disease progression unless one of the above-mentioned criteria is also fulfilled.

Patients with symptoms of rapidly progressing disease without radiological (or photographic) evidence will not be considered to have progressed for efficacy analyses. For patients with bone-only disease, response will be determined *based on radiographic findings or clinical symptoms* (Appendix 7) with the following extension: the overall lesion response at each assessment will be based solely on non-target lesion responses. Specifically, in the absence of new lesions, the overall lesion response at each assessment will be one of the following: CR, SD, unknown (i.e., missing data), or *progressive disease*. All assessments not qualifying for CR, progressive disease, or unknown would be classified as SD. In the presence of any new lesions, the overall lesion response will be progressive disease.

If a patient presents with both irradiated and non-irradiated bone lesions, only the non-irradiated lesions should be followed for tumor assessments unless progression is documented after radiation.

In the event that it is not feasible to perform a bone scan, or it is anticipated that it will not be feasible to perform bone scans throughout the study, F-18 sodium fluoride (¹⁸F NaF) PET scans may be substituted. In this case, an ¹⁸F NaF PET scan must be performed at screening and, in patients with bone-only disease not visible on the CT or MRI scans being performed as part of the tumor assessments, must be repeated at every tumor assessment.

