3.4 OUTCOME MEASURES

3.4.1 Primary Efficacy Outcome Measure

The primary efficacy outcome measure for this study, for all patients as well as the subset of patients with *ESR1* mutations, is as follows:

- PFS, defined as the time from randomization to the first occurrence of disease progression as determined by the investigator per RECIST v1.1 (See [Appendix 7](#)) or death from any cause on study, whichever occurs first

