6.4.1 Primary Efficacy Endpoint

The primary efficacy endpoint is PFS, defined as the time from randomization to the first occurrence of disease progression, as determined by investigator review of tumor assessments using RECIST v1.1 or death on study from any cause. The primary efficacy analyses will be performed on all randomized patients as well as on patients with *ESR1* LBD mutations detected in circulating cell-free DNA, with patients allocated to the treatment arm assigned at randomization.

For patients without disease progression or death as of the clinical data cutoff date, their PFS will be censored at the time of last tumor assessment (or censored at the date of randomization, if no tumor assessment was performed after the baseline visit). For patients who start other anti-cancer treatment prior to the documented PFS event, the primary PFS analysis will include PFS events after other anti-cancer treatment. PFS

sensitivity analysis will be performed, censoring PFS on the last tumor assessment prior to starting other anti-cancer therapy.

The two-sided log-rank test stratified by the stratification factors will be used as the primary analysis. The Kaplan-Meier approach will be used to estimate median PFS for each treatment arm. Cox proportional hazards models stratified by the stratification factors will be used to estimate a hazard ratio and its 90% CI. The results from the unstratified analysis will also be provided.

Exploratory analysis for PFS may be performed on patient subgroups by demographic disease characteristics.

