A lesion identified during the study in an anatomical location that was not scanned at baseline is considered a new lesion and will indicate disease progression.

If a new lesion is equivocal, for example because of its small size, continued therapy and follow-up evaluation will clarify if it represents truly new disease. If repeat scans confirm there is definitely a new lesion, then progression should be declared using the date of the initial scan.

(18)F-Fluorodeoxyglucose Positron Emission Tomography (FDG-PET)

While FDG-PET response assessments need additional study, it is sometimes reasonable to incorporate the use of FDG-PET scanning to complement CT scanning in assessment of progression (particularly, possible “new” disease). New lesions on the basis of FDG-PET imaging can be identified according to the following algorithm:

- A negative FDG-PET scan at baseline with a positive³ FDG-PET scan during the study is a sign of PD based on a new lesion.
- In the case of no FDG-PET scan at baseline and a positive FDG-PET scan during the study:

³ A “positive” FDG-PET scan lesion means one that is FDG avid with an uptake greater than twice that of the surrounding tissue on the attenuation-corrected image.

Appendix 7

Response Evaluation Criteria in Solid Tumors, V 1.1 Modified Excerpt from Original Publication (cont.)

If the positive FDG-PET scan during the study corresponds to a new site of disease confirmed by CT, this will be considered PD.

If the positive FDG-PET scan during the study is not confirmed as a new site of disease on CT, additional follow-up CT scans are needed to determine whether there is truly progression occurring at that site (if so, the date of PD will be the date of the initial abnormal FDG-PET scan).

If the positive FDG-PET scan during the study corresponds to a preexisting site of disease on CT that is not progressing on the basis of the anatomic images, this will not be considered PD.

EVALUATION OF RESPONSE

Timepoint Response (Overall Response)

It is assumed that at each protocol-specified timepoint, a response assessment occurs. [Table 1](#) provides a summary of the overall response status calculation at each timepoint for patients who have measurable disease at baseline.

When patients have non-measurable (therefore non-target) disease only, [Table 2](#) is to be used.

Table 1 Timepoint Response: Patients with Target Lesions (with or without Non-Target Lesions)

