Target Lesions	Non-Target Lesions	New Lesions	Overall Response
CR	CR	No	CR
CR	Non-CR/non-PD	No	PR
CR	Not evaluated	No	PR
PR	Non-PD or not all evaluated	No	PR
SD	Non-PD or not all evaluated	No	SD
Not all evaluated	Non-PD	No	NE
PD	Any	Yes or no	PD
Any	PD	Yes or no	PD
Any	Any	Yes	PD

CR= complete response; NE= not evaluable; PD= progressive disease; PR= partial response; SD= stable disease.

Appendix 7

Response Evaluation Criteria in Solid Tumors, V 1.1 Modified Excerpt from Original Publication (cont.)

Table 2 Timepoint Response: Patients with Non-Target Lesions Only

Non-Target Lesions	New Lesions	Overall Response
CR	No	CR
Non-CR/non-PD	No	Non-CR/non-PD ^a
Not all evaluated	No	NE
Unequivocal PD	Yes or no	PD
Any	Yes	PD

CR = complete response; NE = not evaluable; PD = progressive disease.

^a “Non-CR/non-PD” is preferred over “stable disease” for non-target disease since stable disease is increasingly used as an endpoint for assessment of efficacy in some studies; thus, assigning “stable disease” when no lesions can be measured is not advised.

Missing Assessments and Not-Evaluable Designation

When no imaging/measurement is done at all at a particular timepoint, the patient is not evaluable at that timepoint. If only a subset of lesion measurements are made at an assessment, usually the case is also considered not evaluable at that timepoint, unless a convincing argument can be made that the contribution of the individual missing lesion(s) would not change the assigned timepoint response. This would be most likely to happen in the case of PD. For example, if a patient had a baseline sum of 50 mm with three measured lesions and during the study only two lesions were assessed, but those gave a sum of 80 mm, the patient will have achieved PD status, regardless of the contribution of the missing lesion.

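### Section 4.5.5.1 bars symptom-only progression from the efficacy analyses, then lets clinical symptoms determine response in bone-only disease

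*Combined protocol and SAP*

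**What the plan says.** Section 4.5.5.1 sets the response rules for bone-only disease. On efficacy it states: "Patients with symptoms of rapidly progressing disease without radiological (or photographic) evidence will not be considered to have progressed for efficacy analyses". The sentence that follows says response in these patients is determined "based on radiographic findings or clinical symptoms", cites Appendix 7, and adds an extension under which "the overall lesion response at each assessment will be based solely on non-target lesion responses". Progressive disease is one of the categories this produces.

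The endpoint text elsewhere is radiographic:

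- Section 3.4.1 defines PFS by "disease progression as determined by the investigator per RECIST v1.1", or death.
- Section 6.4.1 repeats this: progression is "as determined by investigator review of tumor assessments using RECIST v1.1". Neither section makes an exception for bone-only disease.
- Section 4.5.5 adds: "The main analysis of the trial will be based on the local radiology review results".

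Section 5.3.5.9, which governs adverse-event recording, treats progression data as efficacy data. It allows clinical progression to rest on symptomatic deterioration in rare cases, while asking for objective documentation.

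**The concern.** Two adjacent sentences give different answers to one question: does a bone-only patient whose symptoms worsen, without supporting images, have a progression event? The first says no for efficacy. The second, which is not limited to treatment decisions and defines the response categories, says this can be so.

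The answer matters because investigators know the treatment assignment (Section 4.2). Section 3.3.4 acknowledges the resulting risk of bias and responds by holding scans centrally for possible independent review. A progression call with no imaging evidence behind it cannot be corroborated in that way. Bone-only patients are eligible (Section 4.1.1) and are excluded from neither PFS (Section 6.4.1) nor CBR (Section 6.4.2.3). Two sites, each following one of the sentences, could classify the same patient differently.

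**Working it through.** The plan gives no figure to reproduce on this point, so the check sets the texts side by side.

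| Place | What it governs | Can symptoms alone give progression? |
|---|---|---|
| 4.5.5.1, efficacy sentence | Efficacy analyses | No |
| 4.5.5.1, next sentence | Bone-only response, including progressive disease | Yes, as written |
| 4.5.5.1, extension | Overall lesion response | No: non-target lesions only |
| 3.4.1 and 6.4.1 | PFS | No: RECIST v1.1 |
| 4.5.5 | Main analysis | No: local radiology review |
| Appendix 7 | Timepoint response | No |
| 5.3.5.9 | Adverse-event recording | Yes, in rare cases |

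**Appendix 7, which the disputed sentence cites.** The appendix has a rule for this situation, introduced by "When patients have non-measurable (therefore non-target) disease only", and sends the reader to its Table 2, "Timepoint Response: Patients with Non-Target Lesions Only". That table has 5 rows. Two give progressive disease: unequivocal progression of non-target lesions, and any status with a new lesion. None of the 5 uses symptoms. The special notes on response assessment add that symptomatic deterioration does not describe an objective response, and that such patients are still classified from their lesions.

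**The disputed sentence against itself.** It admits symptoms, yet relies on an appendix without a symptom route and bases the overall lesion response on non-target lesions alone.

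**Which endpoints are exposed.**

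- PFS: yes, because a symptom-only call of progressive disease would be an event.
- CBR: yes, if the call comes before 24 weeks from randomization, because it would end a stable-disease or response status that might otherwise have counted.
- ORR: no, because Section 6.4.2.1 restricts that analysis to measurable disease and so leaves out bone-only patients.
- Duration of response: no effect is claimed.

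**Who is exposed.** The clause is in italics, which the amendment rationale says mark substantive new text in Version 2. If it applies only from Version 2 onward, it reaches only bone-only patients still progression-free at that point and, for CBR, only those not yet at 24 weeks.

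**Size.** The number of disputed events is the number of such patients multiplied by the share with a symptom-only call. The documents give neither, nor the number enrolled when accrual stopped. The planned 152 patients and 95 PFS events are not a usable base after the halt, so no effect size is given.

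**Two neighbouring inconsistencies.**

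- Treatment continuation: the Synopsis and Section 3.1 in one place continue treatment until progression is documented radiographically. In another place, for patients remaining on study, they accept radiographic or symptomatic progression. Section 4.5.11.3 requires radiographic confirmation of progression judged clinically.
- Bone scans: for bone-only disease not visible on CT or MRI, Section 4.5.5.1 calls for a bone scan at each tumor assessment. Footnote n of Appendices 1 and 2 calls for one when clinically indicated.

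**The case against.** The strongest reply is that the efficacy rule is already settled. Only the first of the two sentences mentions efficacy analyses, and it excludes symptom-only progression. The progression criteria that Section 4.5.5.1 lists for lytic or mixed lesions are all lesion-based, and even a pathologic fracture does not count unless one of them is also met. The Appendix 7 citation and the restriction to non-target lesions can be read as limits on the symptom clause. Section 4.5.11.3 requires radiographic confirmation of clinically judged progression by the discontinuation visit and before new anti-cancer therapy. An analyst would have to override several passages to count a symptom-only event.

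Most of this stands as evidence of which sentence is the outlier, and it reduces the likely number of disputed events. It does not remove the conflict: the second sentence carries no limit to treatment decisions, and investigators apply it before an analyst sees the data.

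Three further points stand in part:

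- Treatment continuation and bone-scan frequency are separate from the efficacy definition. The bone-scan difference is also narrower than it looks, because under Version 2 tumor assessments themselves follow institutional guidelines and clinical indication. Both belong in a separate reconciliation.
- A reference to RECIST v1.1 does not settle one label. The bone-only extension uses stable disease, whereas the footnote to Appendix 7 Table 2 advises against that term when no lesion can be measured. The extension is an express departure and can stay as one.
- The row count in Table 2 shows what the criteria allow. It is not an effect size.

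**Conclusion.** The concern holds and is minor. Section 4.5.5.1 contradicts itself on whether symptoms alone can establish progression in bone-only disease. For efficacy, the symptom clause is the outlier against both PFS definitions, the local radiology basis and Appendix 7. Confidence in the textual conflict is high; no claim is made about its numerical effect.

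The practical reach is small. Development is halted and Section 2 states that the primary objectives will not be met. Both schedules mark a tumor assessment at study drug discontinuation, so many symptom calls can be checked against a scan. The restriction to assessments under Version 2 rests on reading the italics as the amendment rationale describes them. Section 6 still specifies PFS and CBR analyses, and any result reported from them needs a single event definition.

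**What to change.** For efficacy analyses, in Section 4.5.5.1:

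- Replace "based on radiographic findings or clinical symptoms" and the appendix citation after it with: per RECIST v1.1 (Appendix 7). Leave the bone-only extension unchanged.
- Add one sentence: Symptomatic deterioration without radiological or photographic evidence is not a progression event for PFS or CBR.

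Put a matching clarification in Section 5.3.5.9. A sensitivity analysis that counts symptom-only calls is optional and would need those calls to be identifiable in the data.

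The cost is one phrase and one sentence in Section 4.5.5.1 and one sentence in Section 5.3.5.9, with no added visit, scan or data field.

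Separately, the sponsor should reconcile the treatment-continuation wording of the Synopsis, Section 3.1 and Section 4.5.11.3, and the bone-scan wording of Section 4.5.5.1 with footnote n of Appendices 1 and 2. This review takes no position on which of those wordings is right and proposes no clinical rule or schedule. The cost of that step depends on how the sponsor resolves it.
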